The total treatment period was four weeks, with two sessions per week for the first two weeks and one session per week for the last two weeks. Participants reported their sensations using the MGH acupuncture sensation scale (MASS) after the treatment.

Statistical plan

General plan: For all outcomes in this proposal, we will (1) compare resting state functional connectivity (rsFC), cerebral blood flow (CBF), and clinical assessment differences within each group using paired t-tests, and between treatment groups using Analysis of Covariance (ANCOVA); and (2) apply multiple regression analyses to examine the relationships between changes in rsFC/CBF and corresponding clinical outcomes. Additional variables, such as age and gender will be included as covariates to reduce subject heterogeneity.

Resting state functional connectivity analysis

Seed based functional connectivity analysis Seed based rsFC will be applied with CONN toolbox implemented in MATLAB. The pre-processing of fMRI data will include slice-timing correction, realignment, co-registration to subjects' respective structural images, normalization of images to the standard Montreal Neurological Institute template, and smoothing with a 6 mm full width at half maximum (FWHM) kernel. In addition to these steps, we will employ segmentation of gray matter, white matter, and cerebrospinal fluid (CSF) areas for the removal of temporal confounding factors (white matter and CSF). Band-pass filtering will be performed with a frequency window of 0.008-0.09Hz.

To eliminate head motion and artifacts, we will identify outlier time points in the motion parameters and global signal intensity using ART. For each subject, we will treat images (time points) as outliers if composite movement from a preceding image exceeds 0.5 mm, or if the global mean intensity is greater than 3 standard deviations from the mean image intensity for the entire resting state scan.

In addition, 6 rigid body motion parameters, as well as white matter and cerebrospinal fluid (CSF) signals will be regressed out, and images will be normalized using structural image unified segmentation and then re-sampled to 2-mm cubic voxels. After linear de-trending, data will be filtered using a temporal band pass (0.01-0.08 Hz) to remove low frequency

noise and influences of higher frequencies reflecting cardiac and respiratory signals, and finally smoothed using a full width half maximum of 6 mm.

In this study, we will use several seed regions. The first seed region is the bilateral PAG (spheres with 2 mm radius on left and right side, peaks of MNI coordinates $\pm 4 -26 -14$). It will allow us to elucidate the involvement of the descending pain modulation system. The second seed region will be bilateral M1. The reason we chose this location is based on 1) a previous study, where we found this area to show significant differences in functional connectivity between cLBP patients and healthy controls and 2) its proximity to the center of the tDCS location in this study.

Then, the averaged time course will be obtained from the seeds and correlation analysis will be performed in a voxel-wise way to generate the functional connectivity map. The correlation coefficient map will be converted into a Fisher-Z map using Fisher's r-to-z transformation to improve the normality.

Group analysis will be applied using the random effects model. A full factorial design module in SPM12 will be applied with four treatments and two time points (before and after treatments). Specifically, we will compare the pre- and post-treatment PAG rsFC (and the control seed) and M1 rsFC differences across different treatments. ACOVA analyses will be applied between PAG rsFC changes (pre- minus post-treatment) and the corresponding clinical assessments and QST changes respectively. A threshold of $p < 0.005$ and $p < 0.05$ small volume corrected will be applied for the regions of interest (ROIs). A threshold of $p < 0.005$ uncorrected and $p < 0.05$ Family-wise Error (FWE) corrected threshold will be used for non-ROIs. The ROIs include: ACC, MPFC, MCC, insula, S2, DLPFC, and parietal lobule.

ASL data analysis

ASL data will be collected before and after the first and last treatments. Data analysis will be applied using a method applied in our previous studies. The pre-statistical processing for each subject will include head motion correction, skull stripping using FSL's Brain Extraction Tool (BET), smoothing with a Gaussian 5 mm FWHM filter to reduce spatial variability, and a 100 s high-pass temporal filtering. In order to quantify perfusion (CBF), even and odd images will be subtracted (60 pairs) and averaged to produce an average CBF-weighted image. Quantification of perfusion will then be performed using a single compartment model that assumes a well-mixed single compartment model. Group analysis will be applied using ANOVA. The same threshold used for the rsFC data analysis mentioned above, will be applied.

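### The ASL section plans ANOVA for CBF where the general plan sets ANCOVA, and no section states that the outcome's own baseline is a covariate

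*Combined protocol and SAP*

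**What the plan says.** The general plan covers all outcomes and lists rsFC, CBF and clinical assessments. It compares each within groups by paired t-tests "and between treatment groups using Analysis of Covariance (ANCOVA"). On covariates it says "Additional variables, such as age and gender will be included as covariates to reduce subject heterogeneity". It will also "apply multiple regression analyses to examine the relationships between changes in rsFC/CBF and corresponding clinical outcomes".

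The section on ASL data analysis gives the CBF group model in one sentence: "Group analysis will be applied using ANOVA". It states no response variable, factors or covariates. On timing it says "ASL data will be collected before and after the first and last treatments". Its one explicit link to the rsFC group analysis is "The same threshold used for the rsFC data analysis mentioned above, will be applied".

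The rsFC section has its own group model: "A full factorial design module in SPM12 will be applied with four treatments and two time points (before and after treatments"). It defines change as pre minus post, but for rsFC only.

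**The concern.** Two sections give different names to the between-group analysis of the same outcome. The more specific one drops the covariates that the general plan promises. An analyst could fit a post-only ANOVA, an ANOVA on change, a group-by-time model or a baseline-adjusted ANCOVA, and claim to follow the document each time.

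The covariate that usually matters most in a pre-post design is the baseline value of the outcome, and no section names it. If it is left out, precision is given away on measurements the trial collects anyway.

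A smaller issue sits beside this. The t-tests, the between-group comparison and the regressions all need one defined CBF change. With four scans there are several candidates. They answer different questions: the acute effect of the first session, the acute effect of the last session, and the effect of the four-week course. A pair left open can be chosen after the results are seen.

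**Working it through.** The documents give no sample size, SD, pre-post correlation or power figure, so there is no planned figure to reproduce. Numbers below that rest on assumptions are marked as such.

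**1. The text side by side**

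| Item | General plan | rsFC group analysis | ASL section |
|---|---|---|---|
| Between-group model | ANCOVA, all outcomes, CBF named | Full factorial, treatment by time | ANOVA |
| Covariates | Age and gender, as examples | None named | None named |
| Own baseline as covariate | Not stated | Pre-treatment scan is a level of time | Not stated |
| Scans defining change | Not stated | Pre and post treatment | Not stated |

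**2. Value of a baseline term**

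Assumptions: equal variance before and after treatment, randomised groups, and pre-post correlation r of 0.3, 0.5 or 0.7. In units of the post-treatment variance:

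- post-only ANOVA: 1
- change score (equivalent to group-by-time with two time points): 2(1 − r)
- ANCOVA on own baseline: 1 − r²
- ratio of ANCOVA to change score: (1 − r²) / [2(1 − r)] = (1 + r)/2

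| r | Change | ANCOVA | ANCOVA / change | ANCOVA / post-only |
|---|---|---|---|---|
| 0.3 | 1.40 | 0.91 | 0.65 | 0.91 |
| 0.5 | 1.00 | 0.75 | 0.75 | 0.75 |
| 0.7 | 0.60 | 0.51 | 0.85 | 0.51 |

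**3. Cost of the extra covariate**

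With four groups, age and gender already in the model, one more covariate inflates variance by about 1 + 1/(N − 8). At an assumed total N of 40, 60 and 100 this is 1 + 1/32 = 1.031, 1 + 1/52 = 1.019 and 1 + 1/92 = 1.011. At N = 60 the ratios to the change score become 0.66, 0.76 and 0.87, and those to post-only become 0.93, 0.76 and 0.52.

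**4. Which scans define CBF change**

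The schedule gives 2 × 2 + 2 × 1 = 6 sessions, so the first and last treatments are separate visits. Read plainly, the ASL sentence gives four scans: before and after each of those two. A looser reading gives two: before the first and after the last.

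On the four-scan reading, null trials were simulated with one CBF value per scan and each contrast tested at 5%. Assumed correlations between scans ran from 0.3 to 0.8. Both a 1 df (two-arm) and a 3 df (four-arm) test were used. The chance of at least one false positive was:

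- two course contrasts (pre-first to pre-last, pre-first to post-last): about 7–9%. The independent-test value is 1 − 0.95² = 9.75%; the shared pre-first scan lowers it.
- three contrasts (the two within-session pairs and pre-first to post-last): 13–14%. The independent-test value is 1 − 0.95³ = 14.3%.
- two-scan reading: one pair, so 5%.

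**The case against.** The strongest reply is that nothing has been shown to be omitted. The general plan governs all outcomes, and ANOVA in the ASL section may be shorthand for a factorial model to which the general covariates still apply. Calling age and gender *additional* suggests that something is already in the model, and baseline is the natural candidate. This stands as far as it goes: a reader might infer that the plan rejects baseline adjustment, and the documents do not support that. They leave it unstated, which is enough to ask for the wording but not to claim a loss.

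The precision figures also do not carry over automatically to the imaging analysis. CBF inherits the rsFC thresholds, which include one that is "small volume corrected will be applied for the regions of interest (ROIs"), so the analysis is map-based. Without a voxel-wise baseline term, a difference-map analysis gains nothing over change scores. This stands too. The gain is secured only for clinical scores and for ROI-level CBF summaries, and the plan does not itself describe the latter.

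A reader might go further on scan choice and count all six pairs, C(4,2) = 6, which gives roughly 18–21%. That count includes pairs starting from the post-first scan, for which the plan poses no question. Within-session contrasts, in turn, inflate error only if they are offered as evidence for the same claim as the course effect. The pairing of rsFC and CBF change in the general plan points towards a course effect, and on that view the excess is the 7–9% figure.

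Finally, a reader might conclude that the rsFC factorial model should give way to difference maps. Nothing here shows that model to be wrong.

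**Conclusion.** The point holds in limited form. The mismatch between ANOVA and ANCOVA for CBF is on the page, and so is the absence of any stated baseline covariate. If baseline is not intended, adjusting for it reduces variance by 15–35% against change scores and by 9–49% against a post-only ANOVA, before a covariate cost of about 2%. These figures rest on assumed correlations of 0.3–0.7, equal pre and post variance and an assumed N of 60. If baseline is already in the model, the gain is nil and the correction is editorial.

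The undefined CBF change is a secondary point. It depends on the four-scan reading, and its size (about 7–9% to 13–14% instead of 5%) applies to a single scalar, not to the voxel-wise thresholds in the plan. No section designates CBF as a primary outcome. The change is worth making because it is cheap, but the text does not show that the planned analysis is invalid.

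**What to change.** - In the ASL section, replace ANOVA with ANCOVA, as in the general plan.
- State that the outcome's own baseline is a covariate. For clinical scores and ROI-level CBF, model the post-treatment value on treatment, its own baseline, age and gender.
- For voxel-wise CBF maps, include age and gender, and baseline where the software allows. Claim no precision gain where it does not.
- State whether CBF has two or four scans per person. If four, name one treatment-course contrast as the CBF change and use it in the t-tests, the ANCOVA and the regressions. Make the within-session contrasts secondary. Pre-first to post-last is one option, noting that it includes the last session's acute effect; pre-first to pre-last could then be a sensitivity analysis.
- Keep the pre-minus-post direction of the rsFC section for any change score, and leave the rsFC factorial model unchanged.

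The cost is rewording and model re-specification. No new data are needed, because baseline scans and scores, age and gender are already in the plan. The added covariate costs about 3%, 2% or 1% of variance at an assumed N of 40, 60 or 100. The study protocol section is written in the past tense. If outcome data had already been seen, rewording cannot restore prespecification: label the contrast post hoc and report all pairs.
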